16. ETHICS

16.1. Institutional Review Board or Independent Ethics Committee

An Independent Ethics Committee should approve the final protocol, including the final version of the ICF and any other written information and/or materials to be provided to the patients. The Investigator will provide the Sponsor or CRO with documentation of IRB/IEC approval of the protocol and informed consent before the trial may begin at the trial center(s). The Investigator should submit the written approval to the Sponsor or representative before enrollment of any patient into the trial.

The Sponsor or representative should approve any modifications to the ICF that are needed to meet local requirements.

The Investigator will supply documentation to the Sponsor or CRO of required IRB/IEC's annual renewal of the protocol, and any approvals of revisions to the informed consent document or amendments to the protocol.

The Investigator will report promptly to the IRB/IEC, any new information that may adversely affect the safety of patients or the conduct of the trial. Similarly, the Investigator will submit written summaries of the trial status to the IRB/IEC annually, or more frequently if requested by the IRB/IEC. Upon completion of the trial, the Investigator will provide the Ethics Committee with a brief report of the outcome of the trial, if required.

16.2. Ethical Conduct of the Trial

This trial will be conducted and the informed consent will be obtained according to the ethical principles stated in the Declaration of Helsinki (48th General Assembly, Somerset West, Republic of South Africa, October 2008 [or current version]), the applicable guidelines for Good Clinical Practice (GCP; CPMP/ICH/135/95), or the applicable drug and data protection laws and regulations of the countries where the trial will be conducted.

Good Clinical Practice is an international ethical and scientific quality standard for designing, conducting, recording and reporting trials that involve the participation of human patients. The trial will be conducted in compliance with GCP and the applicable national regulations so as to assure that the rights, safety and well-being of the participating trial patients are protected consistent with the ethical principles that have their origin in the Declaration of Helsinki.

16.3. Patient Information and Consent

The Investigator will explain the benefits and risks of participation in the trial to each patient, the impartial witness and obtain written informed consent. Written informed consent must be obtained prior to the patient entering the trial and before initiation of any trial related procedure. The final, version dated form must be agreed to by the IRB/IEC and must be provided in language readily understood by the patient. In case the patient is unable to read or write, an impartial witness should be present during the entire informed consent discussion. After the patient has orally consented to participation in the trial, the witness' signature on the form will attest that the information in the consent form was accurately explained and understood. The Investigator will retain an original consent form for each patient, signed and dated by the patient or witness, and by the person who conducted the informed consent discussion. The Investigator

will supply all enrolled patients with either a copy of their signed informed consent or, depending upon local requirements, a second original informed consent, signed by both parties.

The consent form may need to be revised during the trial due to a protocol amendment or should important new information become available that may be relevant to the safety of the patient. In this instance, approval should always be given by the IRB/IEC and existing patients informed of the changes and re-consented, as directed by the IRB/IEC and in accordance with its policies and procedures; however, in some instances where an immediate change is necessary to eliminate an apparent hazard to patients, then it would not be necessary for a protocol amendment to receive IRB/IEC review and approval before being implemented. Those patients who are presently enrolled and actively participating in the trial should be informed of the change if it might relate to the patients' willingness to continue their participation in the trial.

With the consent of the patient, the Investigator should inform the patient's primary physician about participation in the clinical trial.

16.4. Patient Data Protection

The ICF will incorporate (or, in some cases, be accompanied by a separate document incorporating) wording that complies with relevant data protection and privacy legislation.

16.5. Investigator Obligations

This trial will be conducted in accordance with the ICH Harmonized Tripartite Guideline for GCP (GCP, 1997); the US Code of Federal Regulations (CFR) Title 21 parts 50, 56, and 312; and European Legislation; and the ethical principles that have their origin in the Declaration of Helsinki.

The Investigator agrees to conduct the clinical trial in compliance with this protocol after the approval of the protocol by the IEC/IRB in compliance with local regulatory requirements. The Investigator and the Sponsor will sign the protocol to confirm this agreement.

16.6. Protocol Signatures

After reading the protocol, each Investigator will sign the protocol signature page and send a copy of the signed page to the Sponsor or representative (Appendix 1). By signing the protocol, the Investigator confirms in writing that he/she has read, understands and will strictly adhere to the trial protocol and will conduct the trial in accordance with ICH Tripartite Guidelines for Good Clinical Practice and applicable regulatory requirements. The trial will not be able to start at any center where the Investigator has not signed the protocol.

17. DATA HANDLING AND RECORD KEEPING

17.1. Inspection of Records

The Investigator will prepare and maintain adequate and accurate source documents to record all observations and other pertinent data for each patient enrolled in the trial.

The Investigator will allow the Sponsor, CRO, and authorized regulatory authorities to have direct access to all documents pertaining to the trial, including individual patient medical records, as appropriate.

17.2. Retention of Records

It is the Investigator's responsibility to maintain essential trial documents (protocol and protocol amendments, completed eCRFs, signed ICFs, relevant correspondence, and all other supporting documentation). The trial site should plan on retaining such documents for approximately 15 years after trial completion. The trial site should retain such documents until at least 2 years after the last approval of a marketing application in an International Conference on Harmonisation (ICH) region and until there are no pending or contemplated marketing applications in an ICH region or at least 2 years after the formal discontinuation of clinical development of the investigational product. These documents should be retained for a longer period if required by the applicable regulatory requirements or the hospital, institution, or private practice in which the trial is being conducted. Patient identification codes (patient names and corresponding trial numbers) will be retained for this same period of time. These documents may be transferred to another responsible party, acceptable to Sponsor, who agrees to abide by the retention policies. Written notification of transfer must be submitted to Sponsor. The Investigator must contact Sponsor prior to disposing of any trial records.

No records should be disposed of without the written approval of the Sponsor.

18. PUBLICATION POLICY, FINANCING, AND INSURANCE

The data generated by this trial are confidential information of the Sponsor. The Sponsor will make the results of the trial publicly available. The publication policy, finance, and insurance information with respect to the Investigator and trial center will be set forth in the Clinical Trial Agreement.

21. OVERVIEW OF KEY CHANGES

The following bulleted list identifies the key changes to the protocol and provides the rationale for each change:

- New contact information
- Change to safety follow up from 75 days to 90-day (± 10 days) Safety Follow-up Visit to ensure adequate collection of adverse events that could be associated with investigational drug. The timing of the visit is based on the estimated time needed to clear the major active metabolites of RPC1063 in the vast majority of patients (ie, 5 half-lives of CC112273 and CC1084037 and accounting for variation of half-life duration in a human population).
- Extended requirements for contraception in females after treatment discontinuation from the 75-day Safety Follow-up Visit to the 90-day Safety Follow-up Visit.
- Updated description of RPC1063 to include major active metabolite CC1084037 compound background

22. DETAILS OF CHANGES FROM THE PRIOR PROTOCOL VERSION

For each change to the protocol text, Table 9 provides the location of the change, the original text, the revised text, and the rationale for the change. Minor editorial changes are not identified.

Table 9: Specific Changes to Protocol RPC01-2201 from Version 4.0 (29 May 2018) to Version 5.0 (24 May 2019)

| Protocol Section(s) | Original Text | Revised Text or New Text | Rationale |
|--|-------------------------------|-------------------------------|------------|
| Protocol Synopsis, Section 7, Table 2, Section 8, Section 9, Section 12, | 75-day Safety Follow-up Visit | 90-day Safety Follow-up Visit | [REDACTED] |
| Title Page | [REDACTED] | [REDACTED] | [REDACTED] |
| Signature Page | [REDACTED] | [REDACTED] | [REDACTED] |

| Protocol Section(s) | Original Text | Revised Text or New Text | Rationale |
|---|--|--|-------------------|
| Section 5.2 RPC1063 | 
RPC1063 is a small molecule compound that selectively and potently activates the sphingosine 1-phosphate 1 receptor (S1P₁) and S1P₅ receptor (S1P₅), although it is more selective towards S1P₁ over S1P₅. In vitro, RPC1063 has little activity on the other S1P receptors, showing half maximal effective concentration (EC₅₀) > 10,000 nM for S1P₂, > 5000 nM for S1P₃, and > 2000 nM for S1P₄. RPC1063 is extensively metabolized in humans with up to 13 metabolites identified in plasma, urine, and feces, including 1 major active metabolite (CC112273) in plasma. The RPC1063 metabolites, CC112273, RP101988, RP101075, and RP101442, show a similar potency and selectivity profile to RPC1063.
 | 
RPC1063(ozanimod) is a sphingosine 1-phosphate receptor modulator, which binds with high affinity selectively to sphingosine 1-phosphate receptor subtypes 1 and 5. RPC1063 causes lymphocyte retention in lymphoid tissues. The mechanism by which RPC1063 exerts therapeutic effects in CD (Crohn’s disease) is unknown but may involve the reduction of lymphocyte migration into the central nervous system.
 
RPC1063 is 10-fold more selective for S1P₁ relative to S1P₅ and has little activity on other S1P receptors (S1P₂, S1P₃, and S1P₄). RPC1063 is extensively metabolized in humans to form a number of circulating active metabolites. In vitro, RPC1063 and its active metabolites demonstrated similar activity and selectivity for S1P₁ and S1P₅. In humans, approximately 94% of circulating total active drug exposure is represented by RPC1063 (6%), CC112273 (73%), and CC1084037 (15%).
 | 
[REDACTED]
 |
| Protocol Synopsis, Table 2, Section 8.1 | | 
Counseling about pregnancy precautions and the potential risks of fetal exposure must be conducted for female subjects of childbearing potential. The Investigator will educate all FCBP about the different options of contraceptive methods or abstinence as appropriate. The subject will be re-educated every time her contraceptive measures/methods or ability to become pregnant changes. The female subject’s chosen form of contraception must be effective by the time the female subject is randomized into the study (for example, hormonal contraception should be initiated at least 28 days before randomization).
 | 
[REDACTED]
 |

| Protocol Section(s) | Original Text | Revised Text or New Text | Rationale |
|--------------------------------|--|---|--|
| Protocol Synopsis, Section 8.1 | Male patients: Must agree to use a latex condom during sexual contact with women of childbearing potential while participating in the study until completion of the 75-day Safety Follow-up Visit. | Removed text | [REDACTED] [REDACTED] [REDACTED] |
| Protocol Synopsis, Section 8.1 | Acceptable methods of birth control in the trial are the following: 
 •combined hormonal (oestrogen and progestogen containing) contraception, which may be oral, intravaginal, or transdermal •progestogen-only hormonal contraception associated with inhibition of ovulation, which may be oral, injectable, or implantable •placement of an intrauterine device (IUD) •placement of an intrauterine hormone-releasing system (IUS) •bilateral tubal occlusion •vasectomised partner •sexual abstinence | Acceptable methods of birth control in the trial are the following: 
 •combined hormonal (oestrogen and progestogen containing) contraception, which may be oral, intravaginal, or transdermal •progestogen-only hormonal contraception associated with inhibition of ovulation, which may be oral, injectable, or implantable •placement of an intrauterine device (IUD) •placement of an intrauterine hormone-releasing system (IUS) •bilateral tubal occlusion •vasectomised partner •complete sexual abstinence | [REDACTED] [REDACTED] |

Table 8. Adverse Event Date Imputation Rules.....	43
Table 9. Definitions of Simple Endoscopic Score for Crohn's Disease.....	45
Table 10. Score calculations, weights, and rules associated with CDAI, its components, and associated endpoints	46
Table 11. GHAS Grading System.....	51
Table 12. Per-CD Segment GHAS Scores Allowed for Histologic Remission.....	52
Table 13. Robarts Histopathology Index (RHI) Grading System.....	52
Table 14. Per-CD Segment RHI Scores Allowed for Histologic Remission.....	53

LIST OF ABBREVIATIONS

Table 1. Abbreviations

Abbreviation or Specialist Term	Definition
5-ASA	5-Aminosalicylic acid
6-MP	6-Mercaptopurine
AE	Adverse event
AESI	Adverse event(s) of special interest
ALC	Absolute lymphocyte count
ALT	Alanine aminotransferase
ANC	Absolute neutrophil count
Anti-TNF	Anti-tumor necrosis factor
AP	Abdominal Pain
AST	Aspartate aminotransferase
AV	Atrioventricular
CD	Crohn's disease
CDAI	Crohn's Disease Activity Index
CI	Confidence interval
CRO	Contract Research Organization
CRP	C-reactive protein
DLCO	Diffusion capacity of the lung for carbon monoxide
DM	Data management
DSMB	Data Safety Monitoring Board
ECG	Electrocardiogram
eCRF	Electronic case report form
FEV ₁	Forced expiratory volume at 1 second
FVC	Forced vital capacity
GHAS	Geboes Histology Activity Score
HBsAg	Hepatitis B surface antigen
hCG	human chorionic gonadotropin
HCV	Hepatitis C virus
HIV	Human immunodeficiency virus
HR	Heart rate
ITT	Intent to treat
LFT	Liver function test
MedDRA	Medical Dictionary for Regulatory Activities
ms	Milliseconds
NRI	Non-responder imputation
OC	Observed cases
OCT	Optical coherence tomography
PFT	Pulmonary function test (FEV ₁ , FVC, and DLCO)
PK	Pharmacokinetic
PT	Preferred term
PYE	patient-years of exposure
RHI	Robarts Histopathology Index
SAE	Serious adverse event
SD	Standard deviation
SES-CD	Simple Endoscopic Score for Crohn's Disease
SF	Stool Frequency
SAP	Statistical analysis plan
SBP	Systolic blood pressure

SDTM	Study Data Tabulation Model
SDTMIG	Study Data Tabulation Model Implementation Guide
SE	Standard error
SI	Standard international
SOC	system organ class
TEAE	treatment-emergent adverse event
ULN	upper limit of normal
USA	United States of America
VZV	varicella-zoster virus
WBC	white blood cell
WHODrug	World Health Organization Drug classification dictionary

3. OBJECTIVES

3.1. Induction Period Primary Objective

To assess endoscopic improvement following treatment with RPC1063.

3.2. Extension Period Primary Objective

To characterize the long term safety of continued dosing of RPC1063.

4. INVESTIGATIONAL PLAN

4.1. Overall Trial Design and Plan

Approximately 60 patients with moderately to severely active Crohn's disease will be enrolled into this trial. Patients who complete the Induction Period will have the opportunity to receive continued treatment with RPC1063 in the Extension Period, provided that the investigator determined using clinical judgement, that the patient should continue into the Extension Period. All patients in the Extension Period will continue to receive RPC1063 1.0 mg daily and may continue treatment through Week 160. During the Extension Period, the investigator should continue to assess the patient's clinical status and based on clinical judgment determine if the patient should continue or withdraw from the trial and receive alternative therapy.

The safety of patients will be monitored by collection of treatment-emergent AEs, AEs of special interest (AESI), serious adverse events (SAEs), AEs leading to discontinuation of investigational drug, physical examinations, vital signs measurements, ECG results, optical coherence tomography (OCT) examinations, pulmonary function tests (PFTs), and clinical laboratory tests.

Patients who discontinue from treatment due to lack of response, AEs, or other reasons, even if alternative treatment is given, will complete an early termination visit and will be followed for 90days for collection of safety data, including lymphocyte recovery, and for the assessment of their disease status.

4.2. Endpoints and Endpoint Definitions

The Simple Endoscopic Score for Crohn's Disease (SES-CD) assesses the degree of inflammation and will be used to evaluate the primary efficacy endpoint. The SES-CD reflects the assessment of mucosal lesions in CD, and grades lesions by location (rectum, left colon, transverse colon, right colon and ileum) using ulcer size, extent of ulcerated surface, extent of affected surface, and presence/type of narrowing. Additional details and scoring algorithms can be found in [Appendix 2](#).

The Crohn's Disease Activity Index (CDAI) is a composite score that is used to measure the clinical activity of Crohn's disease. The CDAI uses a questionnaire with responses scored numerically and weighted. Scores typically range from 0 to approximately 600, with higher scores indicating greater disease activity. The 8 components used to assess the CDAI and their weighting factors along with

the data handling details for deriving the average daily scores (including the sub-scores) over the 7 day period are noted in [Appendix 3](#).

The severity of Crohn’s disease is defined based on CDAI score as follows: mild with CDAI score of ≥ 150 to < 220 , moderate with CDAI score of ≥ 220 to ≤ 450 and severe with a CDAI score of > 450 .

4.2.1. Definitions

Table 2. Key Terms

Term	Definition
SES-CD	The sum of the scores for the 5 segments composed of the sum of 4 separate components that include: Size of ulcers, Extent of ulcerated surface, Extent of affected surface and the presence and type of narrowing. The 4 components are evaluated for each of the accessible segments and are scored as 0 to 3. The segments include: rectum, sigmoid & left colon, transverse colon, right colon and the ileum. The range of SES-CD scores is 0 – 12 for each segment, and 0 – 56 for the overall SES-CD score, with larger scores indicating greater severity of disease.
CDAI	The weighted sum of the 8 components: Number of liquid or soft stools for 7 days, Abdominal pain for 7 days, general well-being for 7 days, presence of complications, taking diarrhea medication, abdominal mass, hematocrit and percentage deviation from standard weight. The typical range of CDAI score is 0 to > 600 .
PRO2	The weighted sum of two items that separately contribute to the derivation of two CDAI sub-scores: $PRO2 = SF*7*2 + AP*7*5$. See Table 10, Appendix 3 for details.
SF/AP	The unweighted sum of two items that separately contribute to the derivation of two CDAI sub-scores: $SF/AP = SF + AP$. See Table 10, Appendix 3 for details. NOTE: This definition is included for reference only; in some clinical trials for Crohn’s disease, this has been used for various endpoints.
SF&AP	SF & AP Remission, defined as Average daily stool score ≤ 3 points AND average daily abdominal pain score ≤ 1 point
GHAS	Geboes Histology Activity Score
RHI	Robarts Histopathology Index

Table 3. Key Endpoints

Category or Shorthand	Label	Definition
Endoscopy	Endoscopic Change	SES-CD change from baseline
	Endoscopic Response-25	SES-CD decrease from baseline of $\geq 25\%$
	Endoscopic Response-50	SES-CD decrease from baseline of $\geq 50\%$
	Endoscopic Remission	SES-CD ≤ 4 points and a SES-CD decrease from baseline ≥ 2 points with no SES-CD sub-score > 1 point
CDAI	CDAI Change	CDAI change from baseline
	SF Change	SF Change from baseline
	AP Change	SF Change from baseline
	CDAI Clinical Response	CDAI decrease from baseline of ≥ 100 points
	CDAI Clinical Remission	CDAI score of <150
PRO2	PRO2 Clinical Response	PRO2 CD decrease $\geq 50\%$
SF&AP	SF & AP Remission	Average daily stool score ≤ 3 points AND average daily abdominal pain score ≤ 1 point
Histology	GHAS Change	GHAS change from baseline
	GHAS Remission	No active inflammation in any measured segment; see Appendix 4 for details
	RHI Change	RHI change from baseline
	RHI Response - by Segment	RHI segment score decrease $\geq 50\%$
	RHI Remission- by Segment	No active inflammation in a measured segment
	RHI Remission	No active inflammation in any measured segment; see Appendix 4 for details
	Global RHI Score	A weighted sum of the worst of each of the four disease components across the four colonic segments; see Appendix 4 for details
Mucosal Healing	RHI Mucosal Healing	Endoscopic Remission combined with RHI Remission
Biomarkers	CRP Change	C-reactive protein change from baseline
	CRP Response-10	C-reactive protein < 10 mg/L
	FCP Change	Fecal calprotectin change from baseline
	FCP Response-250	Fecal calprotectin < 250 mcg/g

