8. SELECTION AND WITHDRAWAL OF PATIENTS

8.1. Patient Inclusion Criteria

To be eligible to participate in this trial, candidates must meet the following inclusion criteria:

1. Male or female patients aged 18 to 75 years, inclusive
2. Diagnosis of Crohn's disease for at least 2 months (prior to Screening) by clinical endoscopic evidence and corroborated by a histology report (Note: histopathology may be performed during Screening if no prior report is readily available).
3. Crohn's disease Activity Index score of 220 to 450 inclusive with an SES-CD score of ≥ 6 . (If disease isolated to ileum, the requirement will be a SES-CD score ≥ 4 .)
4. Average daily stool score ≥ 4 points and/or an average daily abdominal pain score of ≥ 2 points.
5. Patients must meet one of the following criteria:
 - Have an inadequate response or loss of response to at least one of the following Crohn's disease treatments :
 - Aminosalicylates, oral aminosalicylates ≥ 2.4 g/day or ≥ 3 g/day sulfasalazine for at least 4 weeks
 - Corticosteroids, oral prednisone ≥ 30 mg or budesonide ≥ 9 mg for at least 2 weeks or an equivalent (to oral prednisone) of intravenous corticosteroid for 1 week
 - Immunomodulators, oral azathioprine ≥ 1.5 mg/kg or 6-mercaptopurine 0.75 mg/kg (documentation of therapeutic level of 6-thioguanine is also acceptable) or methotrexate ≥ 12.5 mg/week for at least 8 weeks
 - Biologic therapy (TNF α antagonist or vedolizumab only) at an approved labeled dose used for induction therapy for at least 4 weeks or recurrence of disease activity despite scheduled maintenance therapy. (Biologic therapy exposed patients will be capped at 50% of total enrolled patients)
 - And/or have been intolerant to any of the above mentioned therapies (e.g., unable to achieve doses, dose levels, or treatment durations because of treatment related side effects and/or laboratory abnormalities)
6. The following background therapies for Crohn's disease will be permitted on a stable dose:
 - Oral aminosalicylates (e.g., mesalamine, sulfasalazine, olsalazine, balsalazide) at a stable dose for at least 3 weeks prior to Screening endoscopy
 - Prednisone (doses ≤ 20 mg per day) or equivalent at a stable dose (dose ≤ 9 mg per day) for at least 2 weeks prior to Screening endoscopy
 - Budesonide therapy at a stable dose for at least 2 weeks prior to Screening endoscopy

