11.1.7. Efficacy Definitions

Endoscopic

Response: SES-CD decrease from baseline of $\geq 50\%$

Remission: SES-CD ≤ 4 points and a SES-CD decrease ≥ 2 points with no SES-CD sub-score > 1 point

CDAI

Clinical Response: CDAI reduction from baseline of ≥ 100 points

Clinical Remission: CDAI score of < 150

PRO2

Clinical Response: PRO2 decrease $\geq 50\%$

Clinical Remission: Average daily stool score ≤ 3 points AND average daily abdominal pain score ≤ 1 point

Mucosal Healing: Endoscopic remission plus histologic improvement

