5.5.5. Handling of Missing Segmental Scores for SES-CD, GHAS, and RHI

The analyses of change from baseline and the defined responder analyses for SES-CD, GHAS, and RHI, as applicable, will exclude the segments non-evaluable or missing at baseline, regardless of whether or not they become evaluable post-baseline. In addition, any missing segment scores (in the presence of at least 1 non-missing segmental SES-CD score) of SES-CD will be imputed by non-missing score used in the previous visit. This methodology is the primary analysis and will also be referred to as “complete cases” or “paired segments” as only segments scored at both baseline and the repeat endoscopy will be assessed. Exploratory analyses of the SES-CD scores based on available data without any adjustments or imputation will also be performed.

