APPENDIX 2. SIMPLE ENDOSCOPIC SCORE FOR CROHN'S DISEASE (SES-CD)

The simple endoscopy score (SES-CD) assesses the degree of inflammation. The SES-CD assesses the following 4 components: size of ulcers, ulcerated surface, affected surface, and presence of narrowings. Each of these components are scored on a scale of 0 to 3 as outlined below:

Table 9. Definitions of Simple Endoscopic Score for Crohn's Disease

Variable	SES-CD Values			
	0	1	2	3
Size of ulcers	None	Aphthous ulcers (< 0.5 cm)	Large ulcers (0.5 to 2 cm)	Very large ulcers (>2 cm)
Ulcerated surface	None	<10%	10-30%	>30%
Affected surface	Unaffected segment	<50%	50-75%	>75%
Presence of narrowings	None	Single, can be passed	Multiple, can be passed	Cannot be passed

In the SES-CD, each of these 4 components are assessed in the five segments of the ileum and colon: ileum, right, transverse, left (descending and sigmoid), and rectum. The SES-CD is the sum of the individual scores of each of the components across the five segments. Sub-scores for each segment will be derived and used to create SES-CD.

SES-CD sub-scores

- SES-CD rectum
- SES-CD left colon
- SES-CD transverse colon
- SES-CD right colon
- SES-CD ileum

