APPENDIX 4. GEBOES HISTOLOGY ACTIVITY INDEX AND ROBARTS HISTOPATHOLOGY INDEX

The following tables give details of the scoring for the Global Histologic Disease Activity Score (GHAS)^{3,4} and a newly developed scoring system entitled the Robarts Histopathology Index (RHI)⁵. Higher numbers correspond to more inflammation and mucosal damage. For each CD segment, the GHAS score can be treated as a continuous measure on a 16 point scale. For each CD segment, the RHI score can be treated as a continuous measure on a 33 point scale. Scoring for both indices will be performed for each segment (i.e., ileum, right, transverse, left (descending and sigmoid), and rectum) that is visualized and for which biopsy samples are available. Similar to the SES-CD, sub-scores for each segment will be derived.

The eight components used to assess the per-CD segment GHAS score are noted in the table below. The maximum per-CD segment total score is 16.

Table 11. GHAS Grading System

GHAS Descriptors and Levels	
Epithelial damage	0: Normal 1: Focal Pathology 2: Extensive Pathology
Architectural changes	0: Normal 1: Moderately disturbed (<50%) 2: Severely disturbed (>50%)
Infiltration of mononuclear cells in the lamina propria	0: Normal 1: Moderately increase 2: Severe increase
Infiltration of polypmorphonuclear cells in the lamina propria	0: Normal 1: Moderately increase 2: Severe increase
Polypmorphonuclear cells in epithelium	0: Normal 1: In surface epithelium 2: Cryptitis 3: Crypt abscess
Presence of erosion and/or ulcers	0: No 1: Yes
Presence of granuloma	0: No 1: Yes
Number of biopsy specimens affected	0: None (0 of 6) 1: ≤3% (1 or 2 of 6) 2: 33-66% (3 or 4 of 6) 3: >66% (5 or 6 of 6)

1

[REDACTED]

Exploratory GHAS Histologic Remission (no active inflammation in a measured segment) is defined in the following table, where the max overall GHAS score in a given segment must be less than or equal to 8, and each segment meets this standard:

Table 12. Per-CD Segment GHAS Scores Allowed for Histologic Remission

Epithelial damage	0
Architectural changes	0-2
Infiltration of mononuclear cells in the lamina propria	0-2
Infiltration of polymorphonuclear cells in the lamina propria	0
Polymorphonuclear cells in epithelium	0
Presence of erosion and/or ulcers	0
Presence of granuloma	0-1
Number of biopsy specimens affected	0-3

The four components used to assess the per-CD segment RHI score are noted in the table below. The maximum per-CD segment total score is 33.

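### Endoscopic Remission can be met under the SAP's paired-segment rule while a segment scored at the visit, but not evaluable at baseline, shows active disease; the unit of the sub-score cap also needs confirming

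*SAP*

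**What the plan says.** **Definition.** SAP 4.2.1, Table 3, sets three conditions for Endoscopic Remission: SES-CD of 4 or less, a decrease from baseline of 2 or more, and "with no SES-CD sub-score > 1 point". Protocol 11.1.7 has the same three conditions ("points with no SES-CD sub-score" above 1) and does not define the term.

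**Segments counted.** SAP 5.5.5 covers change from baseline and also the responder endpoints: "the defined responder analyses for SES-CD, GHAS, and RHI, as applicable, will exclude the segments non-evaluable or missing at baseline", even when such a segment can be scored later. A missing segment score "of SES-CD will be imputed by non-missing score used in the previous visit", provided at least one segment was scored. SAP 9.2.1 gives an example: rectum and left colon are evaluated at baseline, four colonic segments are available at Week 12, and only rectum and left colon are used. Scores from all available segments, called Robarts Observed Scores, are also planned. SAP 5.5.5 describes analyses on available data, without adjustment or imputation, as exploratory.

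**Unit of the cap.** SAP Table 2 reserves another word for the 0–3 items: "The 4 components are evaluated for each of the accessible segments and are scored as 0 to 3". It gives each segment a range of 0–12. Appendix 2 says "Sub-scores for each segment will be derived and used to create SES-CD" and lists the five segments under the heading for SES-CD sub-scores. Appendix 4 agrees: "Similar to the SES-CD, sub-scores for each segment will be derived".

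**Composite.** RHI Mucosal Healing is Endoscopic Remission together with RHI Remission. Table 3 defines RHI Remission over any measured segment. SAP 5.5.5 and 9.2.2 apply the baseline-segment rule to RHI, without carry-forward.

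**The concern.** Pairing segments suits a change score, because baseline and follow-up then cover the same bowel. Remission is different in kind. Two of its three conditions describe the state at the visit, whatever was seen at baseline. If a segment could not be evaluated at baseline and is scored at Week 12 with active disease, the paired rule removes it from both the total and the cap, and the patient can still be counted as a remitter. The error runs one way: ignoring a scored segment can create a remitter but cannot remove one.

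Endoscopic remission is a protocol-named endpoint at Weeks 12 and 52 and one half of RHI Mucosal Healing. The sample size is justified by the precision of response and remission rates.

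The cap raises a second, smaller question. Read with Appendix 2, it limits each whole segment, scored 0–12, to 1 point. Whether that severity is intended should be explicit, because the other possible unit, the 0–3 component, would pass more patients.

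**Working it through.** **1. The plan's own scale.** Inputs from SAP 5.1: remission 15% (type not stated), n = 60. Half-width = 1.96 × √(0.15 × 0.85 / 60) = 9.0 points, as stated for that rate, or 5.4 patients. One patient is 1/60 = 1.7 points. For scale only, with three patients reclassified one way (Clopper-Pearson, the interval named in SAP 9.4):

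| Remitters | Rate | 95% CI |
|---|---|---|
| 6/60 | 10.0% | 3.8–20.5% |
| 9/60 | 15.0% | 7.1–26.6% |
| 12/60 | 20.0% | 10.8–32.3% |

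Three is an arbitrary number; the documents give no rate of segments unseen at baseline.

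**2. Paired rule.** The segment pattern is that of SAP 9.2.1; the scores are invented.

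| | Rectum | Left | Transverse | Right | Total |
|---|---|---|---|---|---|
| Baseline | 5 | 3 | not evaluable | not evaluable | 8 |
| Week 12, paired | 1 | 1 | excluded | excluded | 2 |
| Week 12, all scored | 1 | 1 | 3 | 6 | 11 |

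Paired: total 2 ≤ 4, decrease 8 − 2 = 6, highest segment score 1, so remission. This holds for either unit of the cap, since a segment total of 1 contains no component above 1. All scored segments: 11 > 4, so not remission.

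**3. Why the observed scores do not settle it.** Take baseline left colon 4 + ileum 8 = 12. At Week 12 the left colon scores 1 and the ileum is not reached. Observed score: total 1, decrease 11, remission. With the ileum carried forward under 5.5.5: 1 + 8 = 9, not remission. The observed scores add newly seen segments but lose unreached baseline segments, so they exchange one misclassification for another.

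**4. Direction of the proposed rule.** The paired set with carry-forward contains every baseline segment. Adding newly scored segments can only raise the total and the highest sub-score. The remission rate can therefore only stay equal or fall.

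**5. The cap as written.** By Appendix 2, Table 9, an ulcer gives at least 1 for ulcer size, 1 for ulcerated surface and 1 for affected surface, so the segment scores at least 3. Under a segment cap of 1, any ulcer in any counted segment fails remission. With k segments scored, the largest total within the cap is k, so the ≤ 4 limit excludes nobody for k = 1 to 4. For k = 5 it excludes only the case of 1 point in every segment.

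Counting possible score patterns (ulcer size and ulcerated surface occur together and imply affected surface), a segment within the cap has 3 patterns. Five segments give 3⁵ = 243, of which 2⁵ = 32 total exactly 5, leaving 211. A component cap leaves 436. With one scored segment the counts are 3 and 6. These are pattern counts, not patient proportions.

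For ileum-only disease, Protocol 8.1 has a separate entry threshold ("If disease isolated to ileum, the requirement will be a SES-CD score" of at least 4). Before the decrease condition, qualifying totals are 0–1 under the segment cap and 0–4 under a component cap. From a baseline of 4, remission needs ≤ 1 or ≤ 2 respectively.

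**6. RHI Mucosal Healing.** A baseline segment not reached at the visit is carried forward in the endoscopic half and absent from the RHI half. If the carried score exceeds the cap, the endoscopic half already fails. The mismatch can change the result only when that segment was within the cap when last scored.

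**The case against.** Paired segments is a deliberate, declared primary method with a worked example, and it keeps like compared with like. The SAP also plans all-segment scores. The rows of SAP Table 6, which give the method for each proportion endpoint, could not be read in the available text. SAP 4.2.3 labels its Endoscopic Response-50 graphs as paired segments, so Table 6 may name segment versions too, and remission may already be tabulated on observed scores. This limits confidence. It does not remove the point, because step 3 shows that those scores are not the needed version.

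On the cap, a reader might infer that the 0–3 components were meant and that the SAP wording is a mistake. The documents do not support that. Appendix 2 defines the term and a programmer can execute it. The SAP's use of sub-score for CDAI items concerns another instrument. The near-redundancy of the ≤ 4 limit is weak evidence of intent: the ≥ 2-point decrease is itself redundant from any baseline of 6 or more under either unit, so the definition carries a redundant condition however it is read.

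On the composite, a reader might infer that the two halves of RHI Mucosal Healing conflict generally. They need not. Table 3 can be read as stating the required condition, and 5.5.5, qualified as applying where applicable, as stating the segments assessed. The carry-forward difference is confined to the narrow case in step 6.

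**Conclusion.** The main point holds at medium confidence: under the stated primary rule, a patient can be classed as in Endoscopic Remission while a segment scored at that visit shows active disease, and the planned observed scores do not correct it. This rests on SAP 5.5.5 applying to Endoscopic Remission as one of the responder endpoints, which is how it reads.

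The size cannot be estimated. Each affected patient is 1.7 points at n = 60. A reader might infer that the reported remission rate is materially inflated, but nothing in the documents shows how many patients, if any, have newly seen segments. The primary endpoint, Endoscopic Change, is unaffected, and the trial is descriptive with no hypothesis tests.

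The unit of the cap is a matter for confirmation. As written it is workable and strict; whether that strictness was intended is not shown. For the composite, only the segment set needs aligning. Overall this should be fixed, as a derivation and reporting matter for a non-primary endpoint.

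**What to change.** - **Segments.** For Endoscopic Remission, apply the ≤ 4 limit and the cap to all segments scored at the visit plus any baseline segment carried forward under SAP 5.5.5. Keep paired segments for the ≥ 2-point decrease, Endoscopic Change and Endoscopic Response. Report paired and all-segment remission rates side by side, with the number of patients who have newly seen segments.
- **Unit.** State in Table 3 whether the cap applies to segment scores or to component scores, and report remission under the other reading as a sensitivity analysis. If components are chosen, rename the Appendix 2 list as segment scores.
- **RHI Mucosal Healing.** Use one segment set for both halves, and say how an unreached baseline segment is treated in each.

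The cost is SAP wording, derivation code and one table; no new data are needed. The segment change can only leave the rate equal or lower it. Choosing components could only leave it equal or raise it, because every pattern within the segment cap is also within the component cap. Appendix 5 shows that Week 12 and Week 52 topline tables existed by SAP version 1.3, so the change must be disclosed as made after them, with both versions shown.
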